13 OUTCOME MEASURES

Primary outcome

Australian Canadian Osteoarthritis Hand Index (AUSCAN) for hand pain subscale 6 months after treatment.

Secondary outcomes

Outcome Measures in Rheumatology Committee and Osteoarthritis Research Society International (OMERACT-OARSI) agreed responder criteria for clinical studies²¹ at 3, and 6 months that combines:

- Global rating of change question (GROC)
- AUSCAN hand function subscale³⁹
- AUSCAN hand pain subscale³⁹

AUSCAN hand pain subscale 3 months after treatment and hand function subscale 3 and 6 months after treatment.

Numerical rating scale for thumb pain and Likert scale for thumb pain frequency at 3 and 6 months after treatment^{40, 41}

EuroQol 5 Dimensions 5-levels⁴² (EQ-5D-5L) questionnaire for quality of life 3 and 6 months

Patient reported outcome information system (PROMIS SF v2 4a) for participation in social roles & activities at 3 and 6 months ⁴³

Pain self-efficacy questionnaire (PSEQ) at 3 and 6 months⁴⁴⁻⁴⁶

Osteoarthritis Quality Indicator Questionnaire⁴⁷ (OA-QI) for quality of care at 3 and 6 months.

Treatment provided beyond the supported self-management programme at 3 and 6 months.

Adherence to treatment: therapy adherence assessment 3 and 6 months ⁴⁸

14 STUDY PROCEDURES

Recruitment

All new patients referred for initial assessment and therapy for thumb base OA at the following NHS sites will be screened for recruitment: Pulvertaft Hand Centre, Royal Derby Hospital; Nottingham City Care, MOSAIC service; Pennine MSK Partnership, Integrated Care; Kings Mill Hospital, Mansfield. Thumb base OA is not an acute condition so there is often a variable waiting time from referral to treatment.

Patient identification

All patients clinically diagnosed with thumb base OA who are referred for initial assessment and therapy, or on a waiting list for initial therapy assessment, will be identified by delegated site staff. They will be given or posted out a study invitation letter and a participant information sheet (PIS). When they are booking their therapy appointment in the normal way for that site (e.g., with a therapist or administrator, in person, by phone or by returning a slip or email) they will be asked if they are willing to consider study participation. If willing to consider being part of the study, the person will be asked pre-screening questions to ensure that they are potentially eligible for the study (i.e., not currently receiving therapy for thumb base OA, not currently part of a research trial). Potentially eligible participants will be booked into a longer research study appointment slot, to allow time for screening, and potential consent and data collection. If a patient is not interested in taking part in the study or is ineligible due to the pre-screening questions, then they will be booked into a routine NHS care slot. If patients are handed the study information at a clinic appointment and they wish to be screened for the study on the same day; this will only happen if they have had adequate time to consider the study (time to read the information and then to ask questions) and to complete informed consent.

Eligibility screening

All patients willing to be considered for the study will have a research appointment to precede their therapy appointment. In this appointment the clinician providing care will take a routine medical history and a routine physical examination to confirm clinical signs of symptomatic thumb base OA. The participant will also be asked to confirm they are available to attend therapy sessions. Where participants are not eligible for the study, or decline to consent, their age, their sex assigned at birth, as well as any reasons for ineligibility (if known) will be collected on an anonymised screening log.

FUNDED BY

NIHR | National Institute for
Health and Care Research

Consent

At the research appointment the treating clinician or a delegated individual will discuss the study in more detail, confirm participants have had sufficient time to consider the study information, and provide further opportunities to ask questions. Participants interested in taking part will then be asked to give consent to participate. All participants must consent to be part of the cohort study. Participants will be asked to consent to the data collected being looked at by researchers and clinical trials unit staff from Keele University.

Participants will be asked if they are happy for us to contact them about other aspects of the study, and this will be used to contact some participants about the interview study (and if further funding and ethical approval is secured, to extend the follow up by adding a further follow-up questionnaire beyond six months). It is possible to opt out of interviews but still participate in the cohort. All collaborators taking informed consent will have undertaken Good Clinical Practice (GCP) training. Consent will be taken in two ways according to participant preference, either through a REDCap (Research Electronic Data Capture) generated form sent by email to the participants personal email, and the participant completes the form online with tick boxes to confirm agreement. Or a paper form where the participant signs the form to confirm consent.

At the research appointment, data will be collected after informed consent has been given. A baseline self-reported participant questionnaire will be used to collect patient-rated outcome measures and demographic information of ethnicity, educational level, time since onset of thumb pain, working status, thumb pain and work, and income (table 1). Study specific physical assessments will also be undertaken. The data collected includes measures for pain, function, quality of life and participation, and quality of care which will be collected at all time points, and prognostic factors that will be just collected at baseline (table 1 & 2).

Study assessments

Assessments for the study will take place in person, face to face at baseline, and online (or if not possible by postal questionnaire or phone call) at three and six months (table 1). The options of paper based, and online questionnaires allow participants to choose a preferred method which was requested by PPIE members. Having both options was also important as there is evidence to show that online questionnaires can limit the response from certain groups, making the research less accessible⁵³. Phone call data collection will be used if required e.g., there is a need for interpreting services or for minimum data collection (MDC - where a maximum of three attempts will be made). The primary outcome measure is the Australian Canadian Hand Index (AUSCAN), which is recommended as a core outcome for studies of hand OA⁵⁴. It is a patient-rated, disease-specific, and hand-specific questionnaire comprising of five items measuring hand pain (0-20), one item

FUNDED BY

NIHR | National Institute for
Health and Care Research

measuring stiffness (0-4), and nine measuring hand function (0-36). The total score ranges from 0-60 with higher scores indicating more pain, stiffness, or functional limitation. The AUSCAN is both reliable (intra-class correlation co-efficient: 0.85-0.9) and responsive (standardised response mean >-0.7) in patients with hand OA⁵⁵. The AUSCAN has evidence of construct validity as an instrument for use in thumb OA^{56, 57}, while the relevance of pain as the primary symptom of concern, and of the AUSCAN to thumb OA, has been supported by PPIE review for this study. In addition, we will use a numerical rating scale (NRS) specific to thumb pain severity over the last week⁴⁰, to support comparisons with other studies in this area. The temporal features of pain is an important measure in chronic pain conditions⁴¹, and thumb pain frequency is not a concept captured by the AUSCAN, this will be assessed using a Likert scale⁵⁸. Pain self-efficacy will be assessed to judge the impact of education on beliefs about pain, and whether supported self-management gives the confidence to continue the important social and practical activities and work around the pain. This will be measured using the PSEQ⁴⁶, a reliable and valid measure of self-efficacy in chronic pain conditions.

Generic health status and quality of life measures will allow evaluation of general health outcomes, and comparisons with other health conditions. These will be measured using the EuroQol 5 Dimensions 5 Levels (EQ-5D-5L) index questionnaire⁴². Social participation and difficulty in daily life will be measured using the PROMIS short form⁵⁹. A global rating of change (GROC) question is included, enabling calculation of the OARSI-OMERACT responder criteria, which also relies on (absolute and relative) changes in AUSCAN score²¹. The Osteoarthritis Quality Indicator (OA-QI) questionnaire will be used to assess patient-perceived quality of care⁶⁰.

Candidate prognostic factors for response to conservative management will be collected at baseline only. These factors have been identified from a systematic review of the prognosis for pain and function in hand and thumb base OA⁶¹. Additionally, some factors have been identified from treatment cohorts looking at response to treatment in thumb base OA^{62, 63} details of all the assessments are in table 2. The prognostic factors fall into the following categories clinical signs, general health, psychological factors, and perceived symptom severity.

Table 1 Assessments at each study time point

Assessments	Baseline	3 months	6 months	Measurement method
AUSCAN	x	x	x	Participant self-report
Pain NRS	x	x	x	Participant self-report
Pain Frequency	x	x	x	Participant self-report

FUNDED BY

NIHR | National Institute for
Health and Care Research

EQ-5D-5L	x	x	x	Participant self-report
OA-QI	x	x	x	Participant self-report
PROMIS SFv2 4a Participation	x	x	x	Participant self-report
PSEQ	x	x	x	Participant self-report
B-IPQ	x			Participant self-report
Grip strength	x			Clinician assessment
Number of painful joints	x			Clinician assessment
Confirmation of thumb OA & presence of co-existing hand conditions	x			Clinician report
Availability of radiographs	x			Clinician report
Demographic: DOB, sex assigned at birth, ethnicity, language*, work status, income, educational level, postcode, hand dominance.	x			Participant self-report
Health: age at onset of thumb pain, duration of OA thumb, side affected, previous therapy treatment, co-morbidities, BMI*, use of NSAIDs	x			Participant self-report
START psych subscale	x			Participant self-report
GROC		x	x	Participant self-report
Therapy adherence questionnaire		x	x	Clinician and Participant self-report
Number of therapy appointments attended		x		Clinician report
Information regarding additional treatments provided as part of stepped care.		x	x	Clinician and Participant self-report

Key: NRS - numerical rating scale, EQ-5D-5L - EuroQol 5 Dimensions 5 Levels Questionnaire health status and quality of life, OA-QI - Osteoarthritis (care) Quality Indicator, PROMIS SFv2 - Patient-Reported Outcomes Measurement Information System Short Form for participation in social roles and activities, PSEQ - pain self-efficacy questionnaire, DOB - date of birth, BMI - body mass

FUNDED BY

NIHR | National Institute for
Health and Care Research

index, NSAIDS – non steroidal anti-inflammatory medication, GROC – global rating of change question, B-IPQ – Brief Illness perception questionnaire.

*BMI, participants first language and whether an interpreter is needed, are self-report collected in clinician DCF (not baseline questionnaire).

Table 2: Details of (Potential) Prognostic Factor Assessments

Concept	Measurement method	Detail
Perceived symptom severity		
Hand Pain	Australian Canadian Hand Index (AUSCAN) Participant self-report	Pain subscale – 5 items about the severity of pain at rest and with function in the last 48 hours.
Hand Function	AUSCAN Participant self-report	Function subscale – 9 items about the extent of difficulty with different tasks.
Psychological factors		
Mood and perception of condition	STarT back psychological subscale ⁶² Participant self-report	5 items asking about their perception of the condition and the pain.
Illness perceptions	Illness perceptions questionnaire (brief IPQ) ^{64, 65} Participant self-report	8 items on illness perception relating to consequences, timeline, personal control, treatment control, identity, concern (emotional), Illness comprehensibility and Emotions.
General Health		
Age & age at onset	Single item questions Participant self-report	Date of Birth and How long have you had your thumb pain? Less than a year, 1-2 years, 3-4 years, more than 4 years.
Co-morbidities including high BMI	Single-item questions Participant self-report	Have you been given a diagnosis by a health professional of any of the following? knee OA, heart or cardiovascular disease, diabetes (Y/N).

FUNDED BY

NIHR | National Institute for
Health and Care Research

		Self-reported height and weight.
Use of NSAIDs	Completed as part of OA-QI Participant self-report	Single question in OA-QI If you use anti-inflammatory medications have you been given warnings about the side effects? (Y/N/Not Applicable).
Clinical signs		
Number of painful joints in the hand (disease activity)	Hand diagram – participant and clinician identify and count the number of painful joints.	Mark the circles over the joints (with an x) to indicate which joints have been painful on most days of the past month. Please count how many joints are painful.
Hand grip strength	GripAble Dynamometer (kg)	The maximum value of the mean of three right and three left hand measurements.
Additional Factors to consider		
Co-existing hand conditions	Routine clinical assessment	From your clinical assessment does this participant have a symptomatic co-existing hand condition? If yes please indicate which condition(s): Carpal tunnel syndrome, De Quervain's syndrome, Trigger digits, OA wrist (excluding STTJOA considered part of thumb OA), (Y/N). Other, please specify.

Follow-up assessments

At three and six months, questionnaires will be sent to participants by email or post according to participant stated preference. These questionnaires will collect outcome data on hand pain and function, global rating of change, quality of life, quality of care and adherence to treatment.

If participants do not respond to the questionnaire, a further one will be sent after two weeks, if after a further 2 weeks there is still no response, contact will be made by phone by a member of the research team (where the participant has previously provided consent for telephone contact). In this call the participant will be asked if they are happy to complete minimum data collection (MDC), by telephone (or post/email if preferred). MDC comprises 15 questions: The AUSCAN pain and function score and a global rating of change.

If contact cannot be made (maximum three attempts over 2 weeks during working hours (9am to 5pm) on weekdays), an MDC form will be sent by post. There will be no further attempts to collect data at this time point. Participants can withdraw from the study (data previously collected will remain in the study database and be used for de-identified analysis) at any time point including when contact is made by telephone.

Those who participate in the study and return either a paper or online questionnaire at 6 months will be included in a prize draw for the opportunity to win one of eight £25 prizes (e.g. Love2Shop voucher).

Patient involvement has highlighted the importance of longer-term outcomes in this chronic condition. If further funding can be gained, the study team would seek permission to contact participants and determine longer-term outcomes (for change in pain, hand function, participation, pain self-efficacy and quality of life). In the consent forms there will be a section on consent to further contact which would be used for this purpose.

Qualitative Research – Linked Study

The aim of the interview study and focus group is to evaluate the participant experiences of care and identify what factors participants and therapists feel contribute to the outcome of a supported self-management package of care.

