A total of 150 participants will be recruited and, with an anticipated maximum loss to follow-up of 30%, 105 participants would be retained at 6-months. This sample size will enable the proportion of participants meeting the OMERACT-OARSI responder criteria at 6-months to be estimated with a confidence width of 20% (the difference between the lower and upper bound of a 95% confidence interval). The sample size is derived using the Exact (Clopper-Pearson) method. This calculation assumes that the proportion of participants meeting the OMERACT – OARSI responder criteria is 50% (a worse-case scenario for a sample size calculation) but is also reasonable given that 33% - 44% of participants met these criteria in a trial at 3-months where stepped care was not part of the treatment package ¹⁷. Additionally for the secondary objective of investigating the association of prognostic factors with pain and function outcomes. The sample size calculated above (n=105) allows a difference of 0.05 or more in model R2 to be detected at 80% power and 5% significance in a multiple regression to predict our outcomes of interest e.g., (AUSCAN pain or function) when comparing a model with, and without a single predictor of interest. This assumes an R2 value of 0.3 for the model without the predictor of interest and translates to an effect size (f2) of 0.077 (=0.05/0.65). An R2 value of 0.3 is feasible as, it has been achieved in another study predicting outcome in hand therapy ⁵⁹. The sample size calculations were completed using PASS 2020 software ⁶⁰.

Planned recruitment rate.

It is planned to recruit participants from four study sites that each receive 15-20 referrals per month. From recruitment to a previous study at two of these sites it is estimated that at least 3 participants monthly will consent to the study. With a 14-month recruitment period, a total sample size of 150

consenting participants is considered feasible within the fellowship ($4 \times 3 \times 14 =$ a minimum pool of 168 participants).

Procedure(s) to account for missing or spurious data

The amount of missing data, and the reasons for non-response where given, will be reported. Primary analyses will be based on multiple imputation by chained equations to impute missing data. As a sensitivity analysis, analyses of the primary outcome (AUSCAN) will be re-analysed using only the complete data for comparison⁶⁹.

Qualitative analysis – linked study

Data management and analysis of linked study

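### NSAID use, a candidate prognostic factor, can only be inferred from an item about side-effect warnings, so users and non-users may be misclassified

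*Protocol*

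**What the plan says.** In protocol section 14, Table 1 lists NSAID use among the baseline health variables reported by the participant: "previous therapy treatment, co-morbidities, BMI*, use of NSAIDs". Table 2 repeats it as a potential prognostic factor under general health and gives its source as "Completed as part of OA-QI Participant self-report". The detail column gives one question: "If you use anti-inflammatory medications have you been given warnings about the side effects? (Y/N/Not Applicable").

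The same section states what that questionnaire is for: "The Osteoarthritis Quality Indicator (OA-QI) questionnaire will be used to assess patient-perceived quality of care". It also fixes the timing: "Candidate prognostic factors for response to conservative management will be collected at baseline only".

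Neither table lists a question that simply asks whether the participant uses NSAIDs. The protocol does not say how the three answers become a use variable.

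**The concern.** The item measures whether a user was warned, which is a feature of care. Whether the person uses NSAIDs can only be read from which box is ticked, and No is ambiguous: it can come from a user who was not warned or from a non-user who was never warned.

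Two coding rules suggest themselves, and each can go wrong:

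- **Yes or No means user.** Non-users who tick No rather than Not Applicable are counted as users.
- **Only Yes means user.** Unwarned users are counted as non-users, and the factor becomes warned use, which mixes exposure with quality of care.

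The association of prognostic factors with pain and function is Objective 3 (section 10), and section 19 plans a paper on it. An analysis plan can choose a coding rule, but it cannot recover an answer that was never requested.

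**Working it through.** **The plan's own figure.** Section 15 gives n=105 (150 recruited, 30% loss), a model R-squared of 0.30 without the predictor, a gain of 0.05 and a 5% significance level. It states that this "allows a difference of 0.05 or more in model R2 to be detected at 80% power and 5% significance".

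- f² = 0.05 / (1 − 0.35) = 0.0769, which agrees with the stated 0.077.
- Non-centrality = 105 × 0.0769 = 8.08.
- A partial F test with 1 numerator degree of freedom gives power 0.803 with 6 predictors, and 0.803-0.804 for 2 to 12 predictors. The stated 80% reproduces.

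**Assumptions for the dilution.** The protocol supplies none of these values.

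- p = true proportion using NSAIDs, 0.3 to 0.5.
- s = proportion of users classed as users, 1.00 or 0.95.
- m = proportion of non-users classed as users, 0 to 0.30.
- The error is unrelated to outcome and to the other covariates.

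**Formulas.**

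- Apparent prevalence: q = ps + (1 − p)m.
- Slope retained: (s − m) p(1 − p) / [q(1 − q)].
- R-squared gain retained: φ² = (s − m)² p(1 − p) / [q(1 − q)].
- Observed gain = 0.05 φ², and f² = 0.05 φ² / (0.70 − 0.05 φ²).

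**Worked example** (p=0.3, s=1, m=0.05):

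- q = 0.3 + 0.7 × 0.05 = 0.335.
- φ² = 0.95² × 0.21 / (0.335 × 0.665) = 0.851.
- Observed gain = 0.0425 and f² = 0.0425 / 0.6575 = 0.0647, giving power 0.733.

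**Yes or No read as use** (n=105, 6 predictors):

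| p | s | m | slope retained | observed gain | power |
|---|---|---|---|---|---|
| any | 1.00 | 0 | 1.00 | 0.050 | 0.80 |
| 0.3 | 1.00 | 0.05 | 0.90 | 0.043 | 0.73 |
| 0.5 | 1.00 | 0.05 | 0.95 | 0.045 | 0.76 |
| 0.3 | 0.95 | 0.05 | 0.87 | 0.039 | 0.69 |
| 0.5 | 0.95 | 0.05 | 0.90 | 0.040 | 0.71 |
| 0.3 | 1.00 | 0.30 | 0.59 | 0.021 | 0.42 |
| 0.5 | 1.00 | 0.30 | 0.77 | 0.027 | 0.53 |
| 0.3 | 0.95 | 0.30 | 0.55 | 0.018 | 0.37 |
| 0.5 | 0.95 | 0.30 | 0.69 | 0.023 | 0.46 |

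**Only Yes read as use.** Here m = 0 and s is the share of users who were warned. Taking that share as 40% to 80%, again an assumption, power runs from 0.28 (p=0.5, s=0.4) to 0.67 (p=0.3, s=0.8). Changing the rule changes who is misclassified. It does not remove the error.

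**The case against.** The strongest reply is that the item already has a route for non-users. It is worded conditionally and offers Not Applicable. If every non-user takes that route and Yes or No is read as use, there is no misclassification and power stays at 0.80. Nothing in the protocol says how often respondents would do otherwise. Section 15 leaves the detail to a separate analysis plan, which is a normal place for a coding rule. This part of the reply stands: the size of the problem is unknown and could be nil.

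A reader might infer more than the document supports, in four ways:

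- **That non-users are in fact counted as users and the association is in fact diluted.** No coding rule is stated, and it is not known whether any non-user would tick No.
- **That bias towards no association is certain.** It follows if the error is unrelated to outcome. If those who misread the item differ in ways linked to outcome or to the adjustment variables, the direction in the adjusted model is not guaranteed.
- **That the stated 80% power is wrong.** That statement concerns a generic single predictor. It reproduces, and it does not name NSAID use.
- **That a null result could not be interpreted.** In the scenarios tabulated, 55% or more of the slope survives. The estimate would be harder to interpret and would need a stated limitation.

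The scope is also small. NSAID use is one of several potential factors, section 15 speaks of selected factors, and it calls this objective secondary for sample size purposes.

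What the reply does not meet is the ambiguity of No. A later coding rule cannot separate an unwarned user from a non-user who gave the same answer.

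**Conclusion.** The point holds as a measurement weakness. A candidate prognostic factor is taken from an item about something else, and no direct question on use is listed. Whether the association is diluted, and by how much, cannot be determined from the protocol.

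With assumed use of 30%-50%, 95%-100% of users classed correctly, and error unrelated to outcome and covariates, reading Yes or No as use gives power of about 0.69-0.76 when 5% of non-users tick No and about 0.37-0.53 when 30% do. With no error it is 0.80.

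The effect is confined to this one factor. The primary outcome, the responder proportion and its confidence width, and the general power statement are unaffected. This is a cheap improvement to one variable, and the study's main conclusions do not depend on it.

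**What to change.** Add one direct baseline yes/no item on current NSAID use. The clinician data collection form is a natural place, because the footnote to Table 1 already puts self-reported BMI and first language there. Name the new item in Tables 1 and 2 as the source of the prognostic factor, and keep the questionnaire item for quality of care only.

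For participants already enrolled without the new item, state how Yes, No and Not Applicable are coded and report the limitation. Participants who answer both items would also show how often the two disagree, which would replace the assumed error rates above with observed ones.

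The cost is one extra question and a minor amendment. Because candidate factors are collected only at baseline, the change helps only participants enrolled after it is made.
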